- **Therapeutic Alliance:** The Working Alliance Inventory (WAI)¹⁵⁸ will be used for measuring level of therapeutic alliance at multiple time points during the treatment period. It is a widely-used instrument designed to measure alliance between client and clinician across three dimensions (Task, Bond, Goal), and has strong psychometric properties, including association with alcohol treatment outcome^{204, 205}. Both the client (WAI-C) and therapist (WAI-T) versions will be administered to all participants/clinicians across all treatment conditions. Participants assigned to the CBT4CBT condition will also complete an adapted version designed to assess their level of alliance with the computer program (WAI-Tech), which has been described in a recent report by [name].

- **Cognitive Function: Shipley Institute of Living Scale**

Shipley Institute of Living Scale Shipley Institute of Living Scale Schedule of Assessments

Instrument name	Domain assessed	Scree n/ Pre Tx	Week ly	Mont hly	Post Tx (8 wks)	FU 1, 3, 6 mo
Informed Consent Quiz ^{216, 217}	Informed consent	X				
Screening & Demographics	Description	X				
DSM-5 diagnosis SCID ²¹⁸	Description, diagnosis	X			X	X
Brief Symptom Inventory (BSI) ²¹⁹	Moderator, monitoring	X	X		X	X
Obsessive Compulsive Drinking Scale (OCDS) ²²⁰	Severity, monitoring	X	X		X	X
Timeline follow-back ^{4, 5} w/ BAC	Primary Outcome	X	X		X	X
Urine toxicology screen including ETG ^{199-201, 221} taken on clinic schedule	Outcome	X	X		X	X
Optional Genetics	Exploratory	X				
World Health Organization Quality of Life— Brief ²²²	Quality of life, Outcome	X			X	X
Short Inventory of Problems (SIP) ¹²	Consequences, Outcome	X			X	X
Alcohol Use Dis. Ident. Test (AUDIT) ²²³⁻²²⁷	Description, moderator	X				
Shipley Institute of Living Scale ^{228, 229}	Cog moderator	X				
Stages of Change Questionnaire (SOC) ²³⁰	Motivation, Moderator	X			X	X
Alcohol Risk Response Test (ARRT) ¹⁵	Coping skills, Mediator	X		X	X	X
Change Strategies Inventory (CSI) ^{16, 98, 231}	Coping skills, Mediator	X		X	X	X
CBT Knowledge Quiz ⁵⁰	Knowledge, Mediator	X		X	X	X
Situational Confidence Questionnaire (SCQ) ²³²	Self-efficacy, Mediator	X		X	X	X

Program and Client Costs (PACC-SAT) ^{14, 166, 233}	Tx utilization & cost	X		X	X	X
Yale Adherence & Competence Scale ⁷⁵	Process, Tx integrity		3 sessions/participant			
Working Alliance Inventory (WAI) ²³⁴⁻²³⁷	Process, Tx integrity		Sessions 2, 6			
Endpoint rating form, satisfaction ²³⁸	Evaluation			X		

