C.2.f. Data Management and Analyses

The system of data management will include a combination of scannable forms (Teleforms), direct entry interface (Access), and a relational database (SQL Server) within a closed, secure network, allowing data to flow in a continuous cycle of collection, processing, error checking, and correction on a real-time basis while the study is ongoing. Outlined below is the general strategy for data analyses which will address each of our specific aims. Preparatory analyses will include evaluation of baseline equivalence of groups on demographic and prognostic variables, comparability of rates of data availability and treatment exposure across conditions^{239, 240}, *as well as consideration for the potential contribution of assessment reactivity*^{241, 242}. Data analyses will be conducted on the intention to treat sample, and we will attempt to follow all participants regardless of their retention in the treatment arm of the trial^{179, 180}.

Aim 1 - Evaluation of treatment effects:

The principal strategy for assessing the efficacy of the study treatments on outcome will be random effects regression models for continuously measured *primary* (e.g., percentage of days abstinent - PDA) and secondary (e.g., percentage of heavy drinking days, quality of life, etc.) outcomes. Our research group has used these methods to evaluate main and interaction effects, with appropriate covariates (e.g., retention, compliance with treatment) in multiple previous trials^{121, 138, 142, 171, 172}. *We will include treatment utilization data during the follow-up period as a covariate in analyses evaluating treatment effects through follow-up.*

Analysis of treatment effects at post-treatment and follow-up will include the following contrasts:

- **H1a:** *Main effect for CBT on PDA by month during treatment:* Clinician-CBT and CBT4CBT>TAU.
- **H1b:** *Main effect for CBT on PDA by month through follow-up:* Clinician-CBT and CBT4CBT>TAU.

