Adequacy of sample size: *H1a* – Using conventional effect size estimates, we determined that our proposed sample size of 60 per condition would be sufficient for detecting a small-medium effect ($d=.35$) of treatment on PDA using a random effects regression model (2 groups, PDA by month, 3 data points, ICC=.6, alpha=.05, beta=.80). *H1b* – The proposed sample is sufficient to detect a medium effect ($d=.50$) through the follow-up period with a random effect regression model (2 groups, PDA by month, 7 data points, ICC=.6, alpha=.05, beta=.80). These effect sizes are conservative, based on estimates from completed studies of CBT4CBT^{119, 122}.

Cost-effectiveness analyses: [name] of American University, an expert in cost analyses, particularly of behavioral therapies with substance using populations²⁴³⁻²⁵⁰, is a member of the Scientific Advisory Board as well as a consultant to [name] NIDA-

supported Psychotherapy Development Center. In this capacity, he directs cost-effectiveness evaluations of Center projects, including all those related to CBT4CBT as well as the proposed study. *He was involved in the design of the Program and Client Costs for Substance Abuse Treatment (PACC-SAT)*^{14, 166}, *the instrument that will be used to assess participants use of a wide variety of physical and mental health services, substance use and legal services utilization. The PACC-SAT covers the 12 months prior to randomization, the full-8 week treatment period, and the entire follow-up period* (See Schedule of Assessments). The general approach used to evaluate cost-effectiveness of the protocol interventions will be to evaluate the relationship between value of resources used in intervention implementation (e.g., *costs associated with the facility, staff, and transportation*) and nonmonetary outcomes produced by the intervention (e.g., *reduction in drinking behavior and drinking consequences, improvement in quality of life*). This will include calculating the total cost for each treatment condition, cost per participant in each condition, as well as outcomes of ‘alcohol-free days’, and comparing the average cost per ‘alcohol-free day’ gained per month across treatment conditions, *using strategies outlined in [name] previous work*^{243, 246, 247, 249, 250}.

Aim 2 – Evaluation of skills acquisition as mediator of CBT effects:

[figure not shown]

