The procedures for SAE reporting include written documentation using the clinical notes related to the adverse event and specific forms detailing the event with a sign-off by all appropriate supervisory personnel. Communication of recommendations and decisions from all parties (DSMB, Yale Human Investigations Committee, and MCCA or SATU Administration) are made back to the investigator in a timely manner. We will report all protocol amendments or changes in the informed consent form to NIAAA as well as any temporary or permanent suspension of patient accrual.

- d. For multi-site studies for which the Yale PI serves as the lead investigator: **N/A**
 - i. How will adverse events and unanticipated problems involving risks to subjects or others be reported, reviewed and managed?
 - ii. What provisions are in place for management of interim results?

iii. What will the multi-site process be for protocol modifications?

11. Statistical Considerations: Describe the statistical analyses that support the study design.

Aim 1 - Evaluation of treatment effects:

The principal strategy for assessing the efficacy of the study treatments on outcome will be random effects regression models for continuously measured primary (e.g., percentage of days abstinent - PDA) and secondary (e.g., percentage of heavy drinking days, quality of life, etc.) outcomes. Our research group has used these methods to evaluate main and interaction effects, with appropriate covariates (e.g., retention, compliance with treatment) in multiple previous trials^{121, 138, 142, 171, 172}. We will include treatment utilization data during the follow-up period as a covariate in analyses evaluating treatment effects through follow-up.

Analysis of treatment effects at post-treatment and follow-up will include the following contrasts:

- **H1a:** *Main effect for CBT on PDA by month during treatment:* Clinician-CBT and CBT4CBT>TAU.
- **H1b:** *Main effect for CBT on PDA by month through follow-up:* Clinician-CBT and CBT4CBT>TAU.

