Adequacy of sample size: *H1a* – Using conventional effect size estimates, we determined that our proposed sample size of 60 per condition would be sufficient for detecting a small-medium effect ($d=.35$) of treatment on PDA using a random effects regression model (2 groups, PDA by month, 3 data points, ICC=.6, alpha=.05, beta=.80). *H1b* – The proposed sample is sufficient to detect a medium effect ($d=.50$) through the follow-up period with a random effect regression model (2 groups, PDA by month, 7 data points, ICC=.6, alpha=.05, beta=.80). These effect sizes are conservative, based on estimates from completed studies of CBT4CBT^{119, 122}.

Power calculations	Power	Estimated effect size	# of datapoints	Sample size per cell
H1a: (Clinician CBT + CBT4CBT stand-alone) v TAU, main effect for active treatment	.80	.35	3	60
H1b : (Clinician CBT + CBT4CBT stand-alone) v TAU, main effect for follow up	.80	.50	7	60

Aim 2 – Evaluation of skills acquisition as mediator of CBT effects:

Latent growth curve modeling will be the principal strategy for evaluating mediation using Mplus version 7²⁵¹. The product of coefficients method^{18, 19} will be used to determine the mediating effects of skills acquisition during the treatment period on PDA during follow-up. We will be using the 6-month period following treatment as our alcohol use outcome in this model to support the temporal relation criterion⁶⁴, as well as to evaluate the delayed emergence of CBT's effect on alcohol use¹³⁹. This model will test:

- **H2a:** *Effect of CBT on acquisition of skills (a₂ path: X→M):* Clinician-CBT>TAU; CBT4CBT>TAU
- **H2b:** *Effect of change in acquisition of skills on PDA by month during follow-up (b₂ path: M→Y)*

- **H2c:** *Indirect effect of CBT on PDA via change in acquisition of skills ($a_2 * b_2 / se_{a2} * se_{b2}$)*

Adequacy of sample size: Parameter estimates from our initial trial of CBT4CBT that supported coping skills acquisition as a mediator of treatment effects on substance use⁹⁶ were used to estimate effect sizes of treatment condition on PDA via skills acquisition ($a=.26$; $b=.59$). Based on these effect sizes and power estimates for testing mediation derived from a simulation study⁹⁴, we will have adequate power (.80) to detect significant mediating effects with the proposed sample size of 60 per condition.

SECTION VI: RESEARCH INVOLVING DRUGS, BIOLOGICS, RADIOTRACERS, PLACEBOS AND DEVICES

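### Aim 1 commits to no baseline covariate and does not say how pre-treatment PDA enters the model; using it costs one degree of freedom and helps mainly H1a

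*Combined protocol and SAP*

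**What the plan says.** The Aim 1 text appears twice with the same content: in C.2.f (Data Management and Analyses) and in Section V, item 11 (Statistical Considerations). C.2.f introduces it with "Outlined below is the general strategy for data analyses". PDA is to be analysed by random effects regression. H1a is given as "Main effect for CBT on PDA by month during treatment", and H1b is the matching main effect through follow-up.

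On covariates, the text says that the group's earlier trials used such models "with appropriate covariates (e.g., retention, compliance with treatment", among others. For this trial it makes one commitment: "We will include treatment utilization data during the follow-up period as a covariate in analyses evaluating treatment effects through follow-up". That variable is measured after randomization and concerns follow-up analyses only. No baseline variable is committed to.

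The Schedule of Assessments (C.2.e) marks "Timeline follow-back" as the primary outcome instrument and includes the screening/pre-treatment visit, so pre-treatment PDA will exist for every participant.

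The sample-size paragraph gives H1a as "2 groups, PDA by month, 3 data points, ICC=.6, alpha=.05, beta=.80" and H1b as "2 groups, PDA by month, 7 data points, ICC=.6, alpha=.05, beta=.80". The power table in item 11 describes the H1a contrast as "Clinician CBT + CBT4CBT stand-alone) v TAU, main effect for active treatment", which pools the two CBT arms against TAU, and lists .80 as the power.

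**The concern.** Pre-treatment drinking is an obvious candidate predictor of drinking during treatment, and the model for the primary outcome does not say what is done with it. Treatment lasts 8 weeks (C.2.c, item 3), which gives two on-treatment months. The third H1a data point is therefore probably a pre-treatment month, but the text never says so. The seven H1b points are likewise unexplained: six follow-up months leave one over.

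At least four models fit the wording: pre-treatment PDA ignored, subtracted (change from baseline), used as a covariate, or averaged in as one of the outcome months. Their power for H1a differs widely. Leaving the choice open may give up precision that costs almost nothing, and it allows the primary model to be settled after the data are seen.

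**Working it through.** **Inputs.** From the sample-size paragraph and power table: d=.35 (H1a), d=.50 (H1b), ICC=.6, alpha=.05, 60 per condition, hence 120 v 60 for the pooled contrast. Two treatment months come from the 8-week duration. Assumed: two-sided testing, equal variances over time, no missing data, and r, the correlation between pre-treatment and each post-baseline month, from .2 to .6. The documents do not give r; .6 is the plan's ICC extended to the pre-treatment month.

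**Formulas.** With k post-baseline months, the variance factor of a person's mean is V = (1+(k-1)×.6)/k.
- Pre-treatment PDA ignored: V
- Change from baseline: V+1-2r
- Covariate: V-r²
- Power = Φ(d/√(factor×(1/120+1/60)) - 1.96), where 1/120+1/60 = .025

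**The plan's own figures (.80 each).** Reading the 3 H1a points as three post-baseline months, V=(1+2×.6)/3=.733 and power is Φ(.35/√(.733×.025)-1.96)=.73, or .61 at 60 v 60. Two unstated readings come close to .80: change from baseline with two post months, two-sided, at r=.6 (.82), and the plain two-month mean tested one-sided (.797). For H1b, seven post-baseline points give .97 (120 v 60) or .92 (60 v 60); only a single time point at 60 v 60 comes near (.78). The stated power therefore does not reveal which model was meant.

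**H1a, two treatment months: V=(1+.6)/2=.80.**

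| Use of pre-treatment PDA | Factor | d/√(factor×.025) | Power |
|---|---|---|---|
| Ignored | .80 | 2.475 | .70 |
| Covariate, r=.2 | .80-.04=.76 | 2.539 | .72 |
| Covariate, r=.3 | .80-.09=.71 | 2.627 | .75 |
| Covariate, r=.6 | .80-.36=.44 | 3.337 | .92 |
| Change from baseline, r=.6 | .80+1-1.20=.60 | 2.858 | .82 |

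A random-intercept model that keeps the pre-treatment month as an unconstrained response gives the same contrast as change from baseline, so that row is a model the plan could well produce.

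**Pre-treatment month averaged into the main effect.** There is no arm difference before treatment, so the contrast shrinks to (2/3)×.35=.233. With V=.733 for three points, .233/√(.733×.025)=1.723 and power is Φ(1.723-1.96)=.41.

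**Ordering.** V-r² never exceeds V, and (V+1-2r)-(V-r²)=(1-r)², which is never negative. Apart from one degree of freedom, the covariate is at least as efficient as ignoring or subtracting pre-treatment PDA at every r.

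**H1b, six follow-up months: V=(1+5×.6)/6=.667.** Unadjusted: .50/√(.667×.025)=3.873, power .97. With the covariate: .98 at r=.2, .99 at r=.3 and above .99 at r=.6.

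**The case against.** The strongest reply is that the plan may already use pre-treatment PDA. Three data points in an 8-week treatment suggest weeks 0, 4 and 8; Aim 2 counts its mediator measurements that way, and the pilot (C.1.e) reported a condition-by-time effect on PDA. If the intended model keeps baseline as a response with arm means constrained equal, the covariate adds essentially nothing. This stands as a limit on the gain. It does not close the gap, because these are hints from elsewhere and H1a itself is worded as a main effect.

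The gain over an unadjusted model is also small when r is low (.70 to .72 at r=.2), and the entry threshold for drinking (C.2.b, item 1) could narrow the pre-treatment range and lower r. This stands too.

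The absolute figures assume complete data, while C.2.c, item 4 cites follow-up approaching 90-95%. At 90% (108 v 54), unadjusted H1a power is about .65, and about .70 with the covariate at r=.3. Levels fall, but the ordering does not change. Sidedness is not stated; one-sided testing raises every row.

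A reader might infer that a change-score analysis would leave H1a badly underpowered at low r. The documents do not support this: that reading counts the pre-treatment month among the 3 points, and the plan's single ICC of .6 then implies r=.6, where power is .82. A reader might also want the urn factors and clinic in the model; nothing in the documents lets their benefit be quantified, so that is not part of this point.

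**Conclusion.** The point holds as a low-cost improvement to an under-specified primary model. For H1a, adjusting for pre-treatment PDA raises power from .70 to between .72 (r=.2) and .92 (r=.6) relative to ignoring it, and from .82 to .92 relative to change from baseline at the plan's ICC. It also rules out the averaged-in reading, at .41. These sizes rest on the pooled 120 v 60 contrast, two-sided testing, complete data and an assumed r. The gain is essentially nil if a constrained-baseline model is already intended, and small for H1b in any case.

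It would be tempting to conclude that the stated power of .80 for H1a is wrong. The documents do not support that: sidedness and model form are unstated, and some admissible choices come close to .80. The finding is that the text leaves the choice open, while one choice is never worse than ignoring or subtracting baseline.

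**What to change.** In the Aim 1 text of C.2.f and in Section V, item 11, state that:
1. H1a and H1b test the arm contrast averaged over post-baseline months only (treatment months 1-2; follow-up months 1-6).
2. Pre-treatment PDA enters as a covariate or, equivalently, as a response with arm means constrained equal at baseline.
3. The 3 and 7 data points are made up of named months.

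The cost is one degree of freedom and a few sentences. No new data, visits or participants are needed. If the sponsor already intends the constrained-baseline model, saying so is enough.

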Latent growth curve modeling will be the principal strategy for evaluating mediation using Mplus version 7²⁵¹. The product of coefficients method^{18, 19} will be

used to determine the mediating effects of skills acquisition during the treatment period *on PDA* during follow-up. In this model (Figure 4), M_1 through M_3 are repeated measures (weeks 0, 4, 8) of the mediator ‘acquisition of skills’ (as measured by ARRT¹⁵, CSI¹⁶, homework completion and quality, and knowledge assessment⁵⁰). Both the intercept (I_M) and slope (S_M) act as joint mediators of the effect of X (treatment condition) on Y (PDA during 6 month follow-up), allowing the examination of the average level (i.e., intercept) and average change over time (i.e., slope) of the mediator. We will be using the 6-month period following treatment as our alcohol use outcome in this model to support the temporal relation criterion⁶⁴, as well as to evaluate the delayed emergence of CBT’s effect on alcohol use¹³⁹. This model will test:

- **H2a:** Effect of CBT on acquisition of skills (a_2 path: $X \rightarrow M$): Clinician-CBT>TAU; CBT4CBT>TAU
- **H2b:** Effect of change in acquisition of skills on PDA by month during follow-up (b_2 path: $M \rightarrow Y$)
- **H2c:** Indirect effect of CBT on PDA via change in acquisition of skills ($a_2 * b_2 / se_{a2} * se_{b2}$)

Adequacy of sample size: Parameter estimates from our initial trial of CBT4CBT that supported coping skills acquisition as a mediator of treatment effects on substance use⁹⁶ were used to estimate effect sizes of treatment condition on PDA via skills acquisition ($a=.26$; $b=.59$). Based on these effect sizes and power estimates for testing mediation derived from a simulation study⁹⁴, we will have adequate power (.80) to detect significant mediating effects with the proposed sample size of 60 per condition.

Exploratory Aims:

[figure not shown]

(a) Pre-treatment cognitive function as indicated by measures from CANTAB tasks (sustained attention,

working memory, response inhibition, cognitive flexibility, planning, decision-making) will be evaluated as moderators of CBT's effect on PDA (clinician-delivered CBT and CBT4CBT vs. TAU), using linear moderation regression models, such that a significant interaction between pre-treatment cognitive function measures and treatment condition would indicate a moderated effect (i.e., the effect of CBT on PDA is dependent on levels of pre-treatment cognitive function);

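### Aim 2 calls the growth-curve intercept a mediator without giving a time origin, so the H2c product depends on the coding and the arms' equality at week 0 goes unused

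*Combined protocol and SAP*

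**What the plan says.** Section V, C.2.f (Aim 2) specifies a latent growth curve with "repeated measures (weeks 0, 4, 8) of the mediator", skills acquisition. The intercept and slope both "act as joint mediators of the effect of X", treatment condition, with the outcome being PDA over the six months after treatment. The plan describes the two factors as the "average level (i.e., intercept) and average change over time (i.e., slope) of the mediator". The text states no loadings or time origin. The Aim 2 path diagram (Figure 4) is not shown in the copy available.

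The listed tests use the slope paths only:
- H2a (path a2): "Clinician-CBT>TAU; CBT4CBT>TAU"
- H2b (path b2): "Effect of change in acquisition of skills on PDA by month during follow-up"
- H2c (product of a2 and b2): "Indirect effect of CBT on PDA via change in acquisition of skills"

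On sample size, with a = .26 and b = .59, the plan says "we will have adequate power (.80) to detect significant mediating effects with the proposed sample size of 60 per condition". The Schedule of Assessments in C.2.e puts the first role-play test, coping inventory and knowledge quiz in the screening/pre-treatment column. Section V, item 11 repeats H2a to H2c and the power statement without the sentence on joint mediators.

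**The concern.** A mediator must be something that treatment can move. The first skills wave is taken before treatment. Its order relative to randomisation is not stated outright, but before randomisation is the natural reading. Whether the intercept can be moved therefore depends on where time zero lies, and the text does not say.

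Two things are at stake. First, b2, and with it H2b and H2c, has no fixed meaning until the origin is given. Second, a freely estimated treatment-to-intercept path ignores that randomised arms have the same expected skill at week 0. That costs precision on a2, which is H2a and one of the two factors in H2c.

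**Working it through.** **1. The plan's own figure.** Inputs: a = .26, b = .59, 60 v 60 (N = 120). Two-sided alpha of .05 is assumed, since the plan states .05 for Aim 1 only. In a single-mediator model with unit variance of X and unit residual variances, joint-significance power is power(a) x power(b). The noncentralities are .26 x sqrt(120) = 2.85 and .59 x sqrt(120) = 6.46. Power is .806, so the stated .80 reproduces. That model has one a and one b, with no separate intercept and slope paths.

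**2. What the origin does.** Let one time unit be 4 weeks, and let I and S be the intercept and slope with the origin at week 0. Moving the origin by c gives I_c = I + c*S.
- Treatment to intercept: a1_c = a1 + c*a2. Randomisation gives a1 = 0 in expectation, so a1_c = c*a2.
- Outcome: b1*I + b2*S = b1*I_c + (b2 - c*b1)*S. The slope coefficient becomes b2 - c*b1.
- Total indirect effect: c*a2*b1 + a2*(b2 - c*b1) = a2*b2, whatever c is.

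The total is unchanged, but the slope-only product that H2c names is a2*(b2 - c*b1). It equals the total only if c = 0 or b1 = 0. To illustrate with assumed values, take b1 = .3 and slope variance .10, so b2 = .59/sqrt(.10) = 1.866:
- Origin week 4 (c = 1): 1.866 - .3 = 1.566, and 1.566/1.866 = .84. H2c misses 16% of the indirect effect.
- Origin week 8 (c = 2): 1.866 - .6 = 1.266, and 1.266/1.866 = .68. H2c misses 32%.

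**3. Precision of a2.** The documents give no variance components for the mediator. The only ICC, .6, is for PDA. For t = 0, 1, 2 with residual variance th, the covariance of a person's estimated intercept and slope is G = Psi + th*[[5/6, -1/2], [-1/2, 1/2]], where Psi is the covariance of the true intercept and slope. Imposing equal arms at week 0 gives

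Var(a2, constrained)/Var(a2, free) = 1 - G12^2/(G11*G22).

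Example (assumed): week-0 reliability .6, th = .4, slope variance .10, intercept-slope correlation 0. Then G11 = .6 + .333 = .933, G22 = .1 + .2 = .3 and G12 = -.2. The ratio is 1 - .04/.28 = .857.

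| Assumed covariance | Variance ratio | SE reduction |
|---|---|---|
| Compound symmetry .3 / .5 / .7, no random slope | .604 / .727 / .842 | 22% / 15% / 8% |
| AR(1) .5 / .7 | .615 / .743 | 22% / 14% |
| Random slope: reliability .5-.8, slope variance .05-.20, correlation -.4 to +.2 | .64 to .999 | 20% to 0% |

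The compound-symmetry and AR(1) ratios are identical for origins at weeks 0, 4 and 8, because the free model is the same model under any origin. The standard error of b2 did not change in any random-slope scenario.

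**4. Effect on power.** Take a treatment effect on the slope of .52 slope SD (a = .26 read as half a group difference), reliability .6, slope variance .10 and N = 120. The free SE is sqrt(4 x .3/120) = .100 and a2 = .52 x sqrt(.10) = .164.
- Correlation 0: a2 power rises from .376 to .427, and joint power for a2 and b2 from .272 to .309.
- Correlation -.4: a2 power rises from .376 to .512, and joint power from .263 to .358.

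Over the whole grid, a2 power is .21 to .64 free and .25 to .76 constrained.

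**5. If growth is not linear.** With true arm differences of 0, 1, 1 at weeks 0, 4, 8, the free slope is .50. The constrained slope is .53 (compound symmetry .7) to .57 (compound symmetry .3).

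**The case against.** The strongest reply is that the plan may not mean a week-0 intercept at all. Its gloss of average level fits an origin at week 4, and the missing figure may give the loadings. With that origin the treatment-to-intercept path is a real mid-treatment effect. With the origin at week 8 the intercept is end-of-treatment skill, a sensible mediator. This stands. A reader might infer that the plan tests an impossible path, or that the intercept is invalid under every coding, and the documents support neither. What remains is that a later origin splits one treatment effect across two factors, and H2c counts only one of them.

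It can also be said that H2a to H2c concern change in skills alone and that C.2.f plans a baseline-equivalence check. This stands too. A reader might infer that a chance baseline difference will be reported as mediation, but no intercept-mediation test is listed. The opening for one comes only from the joint-mediator sentence.

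Finally, the precision gain rests on assumed covariances. A reader who used only compound symmetry or AR(1) might infer a gain worth 19 to 66% more participants (1/.842 to 1/.604). The plan specifies a random slope, and with slope variance included the gain can be almost nothing. The constraint also has a cost if growth is not linear, so it is not wholly free.

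**Conclusion.** The specification needs tightening. With a week-0 origin, the intercept path is null by design. With a later origin and linear growth, the intercept duplicates the slope's treatment effect, and H2c as written depends on the coding. Both statements are algebra and rest only on randomisation, a pre-randomisation first wave and, for the second, linear growth.

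The size of the precision gain is not fixed by the documents. Under the assumed structures the variance of a2 falls to between about .60 and .999 of the free model, a standard error about 0 to 22% smaller. H2b gains nothing, and H2c gains only through a2.

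Nor should a reader infer that the constraint delivers the stated .80. That figure belongs to a single-mediator model, and a2 power in the growth model stays below it throughout the assumed grid. This is a cheap improvement to a secondary aim and does not undermine Aim 1.

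**What to change.** In the Aim 2 text of C.2.f, and in Section V, item 11:
- State the loadings, with the origin at week 0.
- Fix the treatment-to-intercept path at zero.
- Keep the intercept as a covariate for the slope and for PDA. Dropping it from the PDA equation would confound b2 wherever starting skill and growth are correlated.
- Define mediation as a2*b2 through the slope only, and delete the statement that the intercept mediates.
- Check the fit of linear growth, and add a sensitivity analysis with week-8 skill given week-0 skill as the mediator.

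The zero constraint belongs with the week-0 origin. Under a later origin it would suppress a real effect and distort a2.

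The cost is a few lines of analysis-plan wording, one model constraint and one extra run. No new data are needed. The statistical downside is the modest shift in the slope estimate under non-linear growth, which the sensitivity run would reveal.
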